 - 4.6 Month 4: The PI and consultant ([name]) will pre-record 3 video-training sessions on study procedures and protocols, caregiver consent process and administration of the PSC survey (in 2020, all clinic personnel at the FQHC partner have already completed a 2-hour online training on how to administer the PEARLS screener)

- 4.7 Month 5: Screeners at each selected clinic will go over the videos for training. The PI and [name] will schedule a follow up 45-min call with each screener to discuss videos and learning/questions.
- 4.8 Months 6 – 7.5: Baseline starts in all five selected clinics. Pre-intervention data will be collected from the clinics over a 10-week period. Clinic staff will be told to follow the ACEs state requirements, which include the PEARLS screenings, ACEs-related health conditions checklist, wellness exam, follow-up education, and mental-health referrals if deemed appropriate. Mediators data will be collected at the end of this period.
- 4.9 Months 7.5 to 30 / Trial starts:
 - 4.9.1 During a 10-week trial period for each clinic (data collection will continue until the end of the trial), each clinic switching from control to intervention status will start using the implementation strategies (i.e., support from the trained implementation coach, TIC workgroup guidance/advise, use of electronic tablets for screenings and service referrals).
 - 4.9.2 Due to the human and financial impact of COVID-19 epidemic, the randomized control clinics had not implemented ACEs screening at the time of the pilot starting. We have identified two clinics within the healthcare system, not part of the trial, that have started implementing ACEs screening. These two clinics will serve as non-randomized comparison groups for this study. We will compare our study clinics and these comparison clinics on ACEs screenings and on referrals to mental health services.
 - 4.9.3 Steps for ACEs screenings with caregivers:
 - 4.9.3.a. When a child and their caregiver come to the clinic for the wellness visit, screening staff will conduct the study screenings using a tablet device that has the REDCap database on it. This should take 10 minutes.

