Quantitative data: We will use descriptive statistics (i.e., frequencies, means and standard deviation estimates) to describe the analytical sample. We will examine whether the implementation strategies (i.e., advisory board, use of REDCap handheld tablets, use of the PSC tool and an implementation coach) increases the number of children screened and referred to support services, compared to baseline. To do that, we will use methodology that accounts for repeated measures over time and that accounts for both within-person and across-person variation (i.e., Generalized linear mixed model (GLMM)) while controlling for clustering of patients within clinics and possible confounding by calendar time. *Our analysis will include sex as a biological variable, testing for a differential effect on outcomes by child sex.* We will report the magnitude of missing data and compare demographic and clinic characteristics and outcomes between observations with versus without missing data. In sensitivity analyses, we will perform multiple calculations (i.e., imputations) using fully conditional specification to obtain 10 complete datasets; summary estimates of intervention effects with 95% confidence limits over the 10 datasets will incorporate within- and between-dataset sampling variability.

Comparison of randomized intervention sites to non-randomized control sites

Due to the human and financial impact of COVID-19 epidemic, the randomized control periods had not implemented ACEs screening at the time of the pilot starting. We have identified two clinics that have implemented ACEs screening that are not part of the trial.

To obtain an additional non-randomized estimate of the intervention effect, we will compare:

- (1) the control periods in the randomized clinics to comparable time periods in the non-randomized clinics;
- (2) the intervention periods in the randomized clinics to comparable time periods in the non-randomized clinics.

We will use the same GLMM models as described above, with indicator variables for non-randomized vs randomized clinic, and randomized control vs intervention periods. Groups will be compared on ACEs screenings, and mental health referral rates.

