Descriptive statistics will be used to describe the sample of children and clinics. The sample will be described using counts and percentages, and treatment groups will be compared using chi-squared tests. We will calculate risk differences with confidence limits for each of our three groups of interest- the study clinics during the control period, study clinics during the intervention period, and the control clinics. For subgroup analyses exploring differences by child demographics, we will calculate risk differences within those subgroups (age, gender, race, and ethnicity).

The reach variable (proportions screened) will be analyzed using binary regression (a generalized linear model, specifying a binomially-distributed dependent variable and identity link function). Modified Poisson regression with robust variance estimation¹⁴ will be used to analyze mental health referrals to estimate adjusted risk differences. Both models will compare the intervention and control arms as the primary independent variable of interest. Possible covariates will include child's sex, age category (<18 months, 18-60 months), child's race (white, black, other/unknown), child's ethnicity (Latino, not Latino, unknown/not reported), language of preference, and study site; covariates will be included in their adjustment changes the intervention regression coefficient by more than 15%.

Models comparing the intervention and comparison clinics will be adjusted for the child's race and for the study site. Missingness in demographic data will be handled by including an 'unknown or not reported' category. Survey data will be analyzed using aggregated intra-class correlations (ICC) to assess within-group agreement, whether clinic care teams shared perceptions of readiness for change during the preparation phase, and implementation climate and leadership. ICC is the variance proportion attributed to care teams.¹⁵ Higher scores in these measures reflect higher organizational support for the translation of a new clinical practice into practice.¹⁶ An agreement of 0.70 or higher reflects an organizational measure.¹⁷

References

1. National Pediatric Practice Community. PEARLS FAQs. Accessed August 14, 2019. <https://nppcaces.org/faqs/>
2. Aware A. ACES Screening Clinical Workflows. Accessed June 15, 2020. <https://www.acesaware.org/wp-content/uploads/2019/12/ACE-Clinical-Workflows-Algorithms-and-ACE-Associated-Health-Conditions.pdf>

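### For H1b and H2b the SAP omits the protocol's time matching and calendar-time control, so part of a change shared by all clinics can enter or mask the strategy effect

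*SAP*

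**What the plan says.** The protocol (section V.c, Data Analysis, under the comparison of randomized with non-randomized sites) plans two contrasts. One sets "the control periods in the randomized clinics to comparable time periods in the non-randomized clinics"; the other sets "the intervention periods in the randomized clinics to comparable time periods in the non-randomized clinics". On the model it says "We will use the same GLMM models as described above", and the model described above it is fitted "while controlling for clustering of patients within clinics and possible confounding by calendar time". The protocol thus has two safeguards: matched periods and a calendar-time adjustment.

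The SAP (Statistical analysis) names three groups for the risk differences: "the study clinics during the control period, study clinics during the intervention period, and the control clinics". The comparison clinics appear as one group with no interval attached. The regression text for this contrast is "Models comparing the intervention and comparison clinics will be adjusted for the child's race and for the study site". The candidate covariates for the main models are sex, age category, race, ethnicity, language and study site; none is a time term. The SAP also replaces the protocol's mixed model with binomial regression for reach and modified Poisson regression for referrals.

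The SAP (Study design) gives three study sites, two comparison sites and seven 10-week intervals, with study sites staying in the intervention phase for several intervals. The protocol (V.1, step 4.8) places a 10-week baseline before any switch: "Baseline starts in all five selected clinics".

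**The concern.** Comparators observed over the same calendar time are valuable because they remove changes that affect every clinic. In a stepped wedge that opens with a baseline, intervention visits come from later intervals. If comparison visits have a different spread over calendar time and the model has no time term, the contrast mixes the strategy with whatever else changed.

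A shared change is plausible here. Both documents describe disruption of the health system by COVID-19, and the SAP adds very high staff turnover. A common recovery in screening or referrals could be read as benefit, and a common decline could hide benefit. The unadjusted risk differences and the subgroup risk differences are exposed in the same way.

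**Working it through.** The documents give no figure for this bias, so there is none to reproduce. The check computes the bias expected when the strategy has no effect.

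**Inputs from the SAP:** 3 study sites, 2 comparison sites, 7 intervals. **Assumptions:** the switch intervals and the intervals covered by the comparison clinics (Figure 1 is not readable), equal visits per clinic-interval, and a linear change D shared by all clinics from interval 1 to interval 7, that is, over 6 steps.

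**1. Unadjusted contrast.** Bias = D × (mean interval of intervention visits − mean interval of comparison visits) / 6. The comparison mean is 28/7 = 4.00 for intervals 1–7, 25/5 = 5.00 for 3–7 and 22/4 = 5.50 for 4–7.

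| Switch intervals | Mean intervention interval | Comparison 1–7 | Comparison 3–7 | Comparison 4–7 |
|---|---|---|---|---|
| 2/3/4 | (27+25+22)/15 = 4.93 | 0.16D | −0.01D | −0.09D |
| 2/4/6 | (27+22+13)/12 = 5.17 | 0.19D | 0.03D | −0.06D |
| 3/4/5 | (25+22+18)/12 = 5.42 | 0.24D | 0.07D | −0.01D |

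For example, if D is a 20-point rise in reach and comparison data cover all intervals, the bias is 3.1, 3.9 or 4.7 points.

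**2. Restriction alone is not enough.** Suppose comparison visits are limited to intervals in which at least one study clinic is in intervention. The bias is then (4.93 − 4.50)/6 = 0.07D for 2/3/4, (5.17 − 4.50)/6 = 0.11D for 2/4/6 and (5.42 − 5.00)/6 = 0.07D for 3/4/5, because intervention visits build up over those intervals and comparison visits do not.

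**3. Site-adjusted model, intervention and comparison visits only.** The arm indicator equals the sum of the three study-site indicators. Five site columns plus one arm column make 6 columns of rank 5, so the arm effect cannot be estimated. Adding interval does not help: the rank is 10 of 11 columns for 2/3/4 and 2/4/6, and 9 of 10 for 3/4/5.

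**4. Site-adjusted model, all visits, no time term.** The comparison clinics now contribute nothing to the intervention coefficient, which becomes a before/after contrast within study sites. For a site switching at interval s, the mean intervention interval is (s + 7)/2 and the mean control interval is s/2. The difference is 3.5 intervals whatever s is, so the bias is 3.5D/6 = 0.58D. With D = 20 points this is 11.7 points.

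**5. With time in the model.** All visits with site and interval indicators give 12 columns of rank 12 and zero bias from the shared change in every schedule tried. Weighting comparison visits to the interval distribution of the intervention visits also gives zero bias, provided that comparison data exist in each of those intervals. With switches at 2/3/4 and comparison data only from interval 3, it leaves −0.035D.

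**The case against.** A reader might infer that the SAP pools every comparison-clinic interval and so discards concurrency outright. The text does not say so. The control clinics are a label in a list of groups, not a rule for selecting data; the protocol's matching rule is not withdrawn, and both cover pages carry the same date. The documents support omission and lack of specification. That does not remove the point: the SAP replaces the mixed model that carried the time control, so this control cannot be assumed to continue.

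A reader might also infer that all of a shared change becomes strategy effect, always in the strategy's favour. The arithmetic shows otherwise. Only part enters, and its sign depends on the direction of the change and on when comparison data were collected. Protocol step 4.9.2 says that the comparison clinics were identified because the planned controls had not begun screening, so observation from interval 1 is an assumption. The baseline statement in step 4.8 describes five planned clinics, whereas the SAP reports three, two of which joined because they had capacity. It supports the timing argument only weakly.

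It is tempting to attach false-positive rates. The documents state neither a significance level nor visit counts for this contrast. They also give no support for a single reach path common to study and comparison clinics, which were at different stages of screening. Moreover, the 0.16D to 0.24D figures belong to the unadjusted contrast, not to the site-adjusted model in the quoted sentence. These objections stand, and no error rate is claimed.

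**Conclusion.** The concern holds in a limited form. For H1b and H2b the SAP carries over neither the protocol's matched periods nor its calendar-time control, and it leaves the comparison-clinic intervals unspecified. Part of any shared change can therefore be credited to the strategy or can mask it.

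The size depends on what is fitted and on a schedule that cannot be read: under the stated assumptions, from a small negative fraction to about a quarter of D for the unadjusted contrast, and more than half of D for a site-adjusted model on all visits without time. On intervention and comparison visits alone, the quoted adjustment with fixed site effects does not identify the arm effect at all. The lack of a time term is textual and does not depend on these assumptions. The SAP should be corrected before H1b and H2b are interpreted.

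**What to change.** In the SAP's paragraph on the comparison-clinic models:

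- State which comparison-clinic intervals enter H1b and H2b.
- Add the 10-week interval, as a categorical term, to both the reach and the referral models.
- Do not combine fixed site effects with an intervention-versus-comparison indicator on intervention and comparison visits alone. Choose one of two models. (a) Fit study-clinic control, study-clinic intervention and comparison-clinic visits together, with site and interval terms. The effect is then the within-site change net of the shared time course, which is not the difference in level that H1b and H2b describe, so the hypotheses should be reworded to match. (b) Follow the protocol's mixed model, with clinic as the clustering (random) effect plus interval and the group indicators. This keeps the comparison of levels, but the clinic variance rests on only five clinics and the clinics' own differences remain.
- For the unadjusted and subgroup risk differences, standardise comparison-clinic rates to the interval distribution of the intervention visits. Leave out intervention visits from any interval without comparison data.

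The cost is a few degrees of freedom and slightly wider limits. SAP Table 1 already defines reach and referrals per 10-week period, so no new data are needed.

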- a. Clinics using implementation strategies will have higher rates of mental health referrals compared to their referral rates before implementing the strategies.
- b. Clinics using implementation strategies will have higher rates of mental health referrals than clinics screening for ACEs and as part of the state funded CALQIC project, without the implementation strategies.
- c. Among children screened, ACEs screenings indicating medium and high risk will lead to mental health referrals at higher rates than screenings indicating low risk.
- d. Exploratory: Are there any differences between in the effect of the implementation strategies on referrals in different sub-groups (such as race, ethnicity, age and gender)?

[figure not shown]
3. Implementation outcomes

- a. Perceive feasibility, acceptability, and usefulness of the intervention will be sufficiently high (see Table 1).

Study design:

Changes to the original study design were needed to accommodate the negative impact that the COVID-19 pandemic had in the partner FQHC system. We conducted a stepped-wedge design (SWD) trial with three sites, with data collection divided into 7 10-week intervals. Study sites remained in the intervention phase for multiple intervals to allow additional data to be collected. In addition to the 3 study sites, 2 additional sites from the same health system served as comparison sites, implementing ACEs screenings without the support of the implementation strategies. See Figure 1 for the SWD schedule.

Figure 1. Stepped-wedge schedule for the ACEs pilot study.

Study sites and patient eligibility:

The study statistician originally selected five clinics from a pool of 16 clinics providing family medicine, pediatric, or primary care for children ages 0 to 5 years old and across five regions to maximize variation (e.g., clinic characteristics such as resources and size). Clinics were located in urban, suburban, rural, and frontier communities. The study PI and FQHC champions invited the identified clinics via email to an informational video session to introduce the study and provided study informational materials to the clinic manager.

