Reach	Measured as a proportion = number of eligible visits in a 10-week period divided by the number of PEARLS and clinical (BPSC/PPSC) screenings. Expect between 80%-92% of eligible children will be screened as threshold; based on pediatric screening studies in primary care. ^{7,8}	EMR system
Mental health referrals	Number of mental health referrals (behavioral analysis, behavioral health, care coordinator, care management, child development/development center or social work) divided by the total # of eligible children in a 10-week trial period. expect 11.4% increased referral rate based on a similar study ⁹ and using current referral rate of 3.8% to inform this threshold [per i2itracks report	EMR system
Changes in BPSC/PPSC	Mean score differences from eligible child visits in each 10-week period. Compare those means in pre vs post implementation periods. No threshold as we will test a two-tail hypothesis for this measure given mixed evidence on the impact of screening policies on access to care and clinical outcomes. ^{10,11} Even if a positive effect is not found, this information is still valuable for implementation and leadership.	EMR system

Measures		
Implementation leadership (ILS)¹²	12-item scale with four subscales measuring proactive leadership, knowledgeable leadership, supportive leadership, and perseverant leadership. Reliability for the total scale is strong ($\alpha=0.98$). An average score of 4+ used as threshold; 5-point Likert scale (not at all-very great extent). Subscale score is based on the mean score for the items; total score is the mean of the subscale scores ¹² ;	Staff provider
Implementation climate¹³	6-item scale measuring the strategic climate for the implementation of interventions. The average interrater agreement: $r^*wg (J) = 0.76$ for the group referenced scale. Items are rated on a 5-item Likert scale (completely disagree-completely agree). Average score of 4+ as threshold ¹³	Staff provider
Covariates		
Child characteristic	Variables include sex, self-identified race and ethnicity, age, language of preference for health care receipt, born in the USA. Note: EMR system does not report data on caregivers of child patients	EMR system

Statistical analysis:

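### The SAP tests within-team agreement with a between-team variance share and an unassigned 0.70 cut-off, so close agreement can fail and poor agreement can pass

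*SAP*

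**What the plan says.** The survey paragraph of the SAP's Statistical analysis section gives the method: "Survey data will be analyzed using aggregated intra-class correlations (ICC) to assess within-group agreement". The question to be answered is "whether clinic care teams shared perceptions of readiness for change during the preparation phase, and implementation climate and leadership". The statistic is then defined: "ICC is the variance proportion attributed to care teams". After a sentence on what higher scores mean, the criterion follows: "An agreement of 0.70 or higher reflects an organizational measure".

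The section gives no formula, no form of ICC (single-rater or team-mean) and no other agreement index. An r_wg-type index appears only in Table 1, where r*wg(J) = 0.76 is listed as a psychometric property of the climate scale.

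Table 1 sets the same target for two of the three constructs, both on 5-category scales. For leadership it says "An average score of 4+ used as threshold", and for climate "Average score of 4+ as threshold". The SAP gives no target for readiness, and the protocol's Instrumentation section confines that measure to baseline. On the number of clinics, the SAP's Study design section says "We conducted a stepped-wedge design (SWD) trial with three sites".

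**The concern.** As defined, the ICC has between-team variance in its numerator. It rises when teams differ from each other and falls to zero when their means coincide, however closely colleagues within each team agree. Whether a team shares a perception is a question about the spread inside that team, which an r_wg-type index measures directly.

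If 0.70 is applied to this ICC, the rule can err in both directions. Three clinics in one health system, all aiming for the same 4+ target, may well have similar means. What is at stake is whether climate, leadership and readiness scores are treated as properties of the clinic or as scattered individual opinion.

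**Working it through.** **The plan's figure.** The 0.70 is a convention. No sample size or power is stated for this analysis, so there is no computed figure to reproduce.

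**Inputs from the documents.** ICC as the variance share attributed to teams; cut-off 0.70; three study clinics; 5-category scales and a 4+ target for leadership and climate.

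**Assumptions (not in the documents).** Within-team SD 0.2 to 1.0; between-team SD 0 to 1.5; 5 to 10 respondents per team; one care team per clinic. Agreement is computed with the single-item r_wg.

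**Formulas.** Let sb be the between-team SD and sw the pooled within-team SD.
- ICC(1) = sb² / (sb² + sw²)
- r_wg = 1 − sw² / 2, where 2 = (5² − 1)/12 is the variance of a uniform response on five points
- ICC(k) = k·ICC(1) / (1 + (k − 1)·ICC(1)), the team-mean form with k respondents

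**Step 1: pass condition.** ICC(1) ≥ 0.70 requires sb² ≥ (0.7/0.3)·sw², so sb ≥ 1.53·sw. At sw = 0.5 that is sb ≥ √(0.25 × 0.7/0.3) = 0.76.

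**Step 2: same agreement, different means.** The variance of the three means is 0, 0.04, 0.25 and 1.00 for the four sets below.

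| sw | r_wg | equal means | 4.0/4.2/4.4 | 4.0/4.5/5.0 | 2/3/4 |
|---|---|---|---|---|---|
| 0.2 | 0.98 | 0 | 0.04/0.08 = 0.50 | 0.25/0.29 = 0.86 | 1/1.04 = 0.96 |
| 0.5 | 0.875 | 0 | 0.04/0.29 = 0.14 | 0.25/0.50 = 0.50 | 1/1.25 = 0.80 |
| 1.0 | 0.50 | 0 | 0.04/1.04 = 0.04 | 0.25/1.25 = 0.20 | 1/2 = 0.50 |

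Within a row, agreement is constant while the ICC runs from 0 to its maximum.

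**Step 3: the 4+ target (climate and leadership).** If all three clinics meet it, their means lie between 4 and 5. The widest spread is 4/5/5 (or 4/4/5), with variance 0.333 and SD 0.577. Then 0.70 needs sw ≤ √(0.333 × 0.3/0.7) = 0.38. This is a limit, because a team with mean 5 is at the ceiling and has no spread of its own.

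**Step 4: both errors in raw ratings, one-way ANOVA estimator, five raters per team.**
- Three teams each rating 4, 4, 4, 4, 5: within variance 0.2, so every r_wg = 0.90. Between mean square 0, within mean square 0.2, ICC(1) = (0 − 0.2)/(0 + 4 × 0.2) = −0.25. Close agreement fails.
- Means 1.4, 3.0, 4.6 with within variances 0.8, 0.5, 0.8: r_wg = 0.60, 0.75, 0.60. Between mean square 12.8, within mean square 0.7, ICC(1) = 12.1/15.6 = 0.78. The rule passes, although two of the three teams fall below 0.70 on agreement.

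**Step 5: team-mean form.** ICC(k) = 0.70 needs ICC(1) of only 0.32, 0.23 or 0.19 for k = 5, 8 or 10. At sw = 0.5, means 4.0/4.5/5.0 and k = 5 give 5 × 0.5/(1 + 4 × 0.5) = 0.83, a pass. Means 4.0/4.2/4.4 give 0.44, and equal means still give 0.

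**Step 6: stability with three teams.** These are simulated proportions from 20,000 datasets per scenario, with three teams of 8 and sw = 0.2:

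| sb | ICC(1) implied | P(ICC(1) ≥ 0.70) | P(ICC(k) ≥ 0.70) | P(all r_wg ≥ 0.70) |
|---|---|---|---|---|
| 0 | 0 | 0.00 | 0.06 | 1.00 |
| 0.2 | 0.50 | 0.13 | 0.69 | 1.00 |
| 0.3 | 0.69 | 0.38 | 0.84 | 1.00 |
| 0.5 | 0.86 | 0.68 | 0.93 | 1.00 |
| 1.0 | 0.96 | 0.91 | 0.99 | 1.00 |

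With sw = 1.0 (r_wg 0.50) and sb = 1.5, the single-rater ICC passes in 0.37 of datasets, while all three teams reach r_wg 0.70 in only 0.01.

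**The case against.** The strongest reply is that the SAP never expressly attaches 0.70 to the ICC. The cut-off stands in its own sentence with its own reference, and it speaks of agreement, the word Table 1 uses for r*wg(J). That is fair, and an r_wg-type index may be what was meant. But then the section gives a cut-off with no statistic to apply it to. The ICC is the only index named there, so an analyst following the text would use it. Either reading needs the same correction.

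A second reply is that the word aggregated may point to the team-mean ICC. The stated variance-share definition favours the single-rater form, but the point stands to this extent: the team-mean form lowers the bar considerably (step 5). It is still zero when team means are equal, so it does not measure agreement either.

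A reader might go further and infer three things that the documents do not support.
- **Teams in near-perfect agreement will fail.** Not so. With within-team SD 0.2, means of 4.0/4.5/5.0 all meet the target and give 0.86. Failure needs means that are close relative to the within-team spread.
- **All three constructs will be judged not shared because the strategy succeeds everywhere.** Readiness is measured only at baseline and has no 4+ target, so it cannot reflect success. For climate and leadership, step 3 shows a constraint and not a certainty.
- **The rule decides which scores can serve as mediators.** The protocol mentions collecting mediators and plans a manuscript on mechanisms. The SAP specifies no mediation model, and neither document makes any analysis depend on passing 0.70.

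**Conclusion.** The mismatch is real. The SAP gives a between-team variance share the task of assessing within-team agreement and leaves its one cut-off without a named index. On the natural reading the rule can give the wrong answer in either direction. At the same r_wg of 0.875 the ICC is 0 with equal means and 0.80 with means 2/3/4. If all three clinics meet the 4+ target for climate or leadership, a single-rater ICC of 0.70 needs a within-team SD of about 0.38 or less, even at the widest possible spread of means.

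The direction of the problem follows from the SAP's own definition. The sizes depend on assumed within-team spreads and team sizes, one team per clinic, and the single-item r_wg. With three clinics the ICC is also unstable: at an implied value of 0.86 the estimate reaches 0.70 in only 68% of simulated datasets. The point is limited to secondary survey measures. Reach, mental health referrals and the feasibility and acceptability hypothesis do not use this rule.

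**What to change.** In the survey paragraph of the SAP's Statistical analysis section:
- Assess within-team agreement with r_wg(J), or r*wg(J) for climate to match Table 1, for each clinic and each scale. Attach the 0.70 cut-off to that index.
- State the formula and the null variance in advance. The choice matters because r_wg(J) rises with the number of items J. With a mean item variance of 1.0 against a null of 2, r*wg(J) = 1 − 0.5 = 0.50. For six items r_wg(J) = 6 × 0.5/(6 × 0.5 + 0.5) = 0.86, and for twelve it is 12 × 0.5/(12 × 0.5 + 0.5) = 0.92.
- Report the ICC separately as a descriptive between-clinic variance share. Name its form (single-rater or team-mean), attach no 0.70 rule to it, and note that an estimate from three clinics is unstable.

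The cost is a change of wording and a few lines of code on the survey data. It needs no new data and adds no burden for participants.
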